#### 3 Data Storage and Confidentiality.

Upon completion of the validation sessions, video/audio data will be transferred to both InnoVital's and the Human Factors Center's secure, password-protected data servers in preparation for data reduction efforts. Recordings will be identified by assigned participant number and will not utilize any identifying participant information, such that each observational session will remain anonymous. No provider identifying information will be collected as part of the research dataset. Access to all study data will be limited to study investigators. Recordings will be kept for three years following the completion of the study so they can be revisited to verify collected data, if necessary, at any point during the FDA pre-market approval process. After three years, the recordings will be destroyed.

#### IV. RISK/BENEFIT ASSESSMENT

1 **Risk Category**. Minimal risk (for subject and participants)

#### 2 Potential Risk.

This study does not involve any interventions or procedures to participants. In the human study, participants are simply identifying a surface anatomical landmark on healthy human volunteer subjects — either with or without a non-invasive device. In the manikin study, participants are only performing cricothyrotomies on manikins. Therefore, risk to participants is minimal, with the greatest risk being a breach of participation confidentiality. Participants can opt out of the study at any time.

Subjects in the human study will lay on tables for 5- to 10-minute durations, expected to occur 5 to 6 times during each day of evaluation. Subjects will have free time in which they are not required to perform any tasks, and frequent opportunities to get up and stretch in the interim. While laying supine, they will have their neck anatomy palpated with light pressure either freehand or with the non-invasive SureCRIC device. The purpose of the palpation is to identify the surface anatomical cricothyroid membrane landmark. A popsicle stick with a round, smooth edge may also be used to note the position of the cricothyroid membrane. Subjects will be asked to report greater than minimal discomfort. Reported greater than minimal discomfort will trigger study termination for that subject. Cooling packs will be made available for subjects should they want to use them for any mild skin irritation or redness. Therefore, risk to subjects is minimal. Subjects can opt out of the study at any time.

#### 3 Protection Against Risks.

To protect against the risks described above, identifying information that can be linked to the participants and subjects is limited to audio and video recordings and heavily protected, not to be shared with any outside parties. For details, please reference Section III-3 Data Storage and Confidentiality.

Participants will be given a consent form explaining the study. Though hospital / health system employees are not specifically being recruited, any participating employee will be made aware that the study is not linked to their employment or employee evaluations, and results will not be shared with hospital administration or leadership. Because adverse event reporting systems are already in place, there is limited risk of an observed adverse event going unreported.

Subjects will be given a consent form explaining the study. Subjects will have frequent opportunities to get up and stretch. Subjects will have break time between sessions and will only actively participate for approximately 5 to 10 minutes during testing sessions (expected

5 to 6 sessions per day). Subjects will be asked to report greater than minimal discomfort. Subjects can opt out of the study at any time. Because adverse event reporting systems are already in place, there is limited risk of an observed adverse event going unreported

### 4 Potential Benefits to the Subjects

Individual participants and subjects benefit from compensation. This study also provides an opportunity for a net benefit, by potentially introducing a useful tool into the medical environment.

## V. SUBJECT IDENTIFICATION, RECRUITMENT AND CONSENT/ASSENT

## 1 Method of Subject Identification and Recruitment.

Recruitment of participants and subjects will be conducted through (a) third-party recruiting companies (e.g., Observation Baltimore), (b) training centers and schools (e.g., Uniformed Services University), and (c) NCHFH and/or InnoVital clinician networks.

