The manikin validation study is one of two parts of the final evaluation method intended to demonstrate the safety and effectiveness of the device, labeling and related materials (e.g., materials, packaging, labeling). From the human factors perspective, the validation study serves to ensure that risks associated with the use of a medical device have been identified and adequately addressed, and that the impacts of residual risks are minimized. InnoVital Systems, Inc. (InnoVital) has engaged the National Center for Human Factors in Healthcare (Human Factors Center) to conduct the validation (also referred to as summative) study for the SureCRIC. Validation conducted by the Human Factors Center will focus on evaluating the use of the device by its intended users in simulated use environments. Specifically, the objectives of the manikin evaluation are:

• Primary endpoint: user-reported interference of the SureCRIC with the tools used for cricothyrotomy. Interference will be defined as problems with or errors caused by the SureCRIC with the use of these cricothyrotomy tools. Assessment for interference will

- be limited to the tools used up to and including the step where the SureCRIC is removed because after this step interference is no longer a concern.
- Secondary endpoints: NCHFH staff will assess the usability of the SureCRIC with the representative kits and tools and document possible procedure interference due to the SureCRIC. NCHFH staff will ask participants about these issues after completion of study participation.

The methods outlined in the protocol were determined based on feedback from the FDA obtained by InnoVital.

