# 5 Vulnerable Subjects.

Though not specifically planned or expected, it is possible that hospital / health system employees will be included as participants. No hospital or health system employees will be included as subjects. Participants and subjects will be protected in two ways. First, no identifying information will be recorded during the study, except for faces of the participants, subjects, and study investigators. Third-party recruiters and administrative staff will coordinate logistics of participants and subjects; therefore, researchers do not need or have access to participants' and subjects' phone numbers or emails. Once participants and subjects have signed their respective consent forms, there will be no connecting information between the person and their participant number or subject number. The data that is collected and analyzed will not contain any identifiers regarding subject name, date of birth or any other identifiers. Secondly, the recruitment material and information letter will make it explicitly clear that participants and subjects are free to end participation at any point in the study.

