# 2 Methods and Data Analysis (Manikin Study)

The study will be a single-arm, open label study. Each of the participants will perform three cricothyrotomy procedures on a manikin. Each procedure will be performed with the SureCRIC and one of three representative cricothyrotomy kits. Participants in the manikin study will complete study sessions that will consist of the following:

- 1. Signing of Documents and Pre-Evaluation Interview (~5 minutes). Prior to study participation, relevant information on clinical experience will be collected from all participants. Sample data points include handedness, years of and nature of clinical experience, cricothyrotomy training with various approaches and kits, and previous cricothyrotomy performance. Upon arrival, participants will be asked to sign an informed consent form that describes participant's role in the evaluation, explains risks involved and consents to the use of audio and video recordings for analysis purposes. Participants will also be asked not to disclose any information about the product or materials they see during the training and evaluation.
- 2. Device Training (approximately 60 minutes). Participants will be introduced to each of the three cricothyrotomy kits as well as the SureCRIC and allowed to practice use on a manikin. SureCRIC training will consist of a review of the Instructions for Use (IFU) and supervised practice following a brief introduction to the device and procedure. A copy of the IFU is attached. Training with the three cricothyrotomy kits will include a review of the kit components and the IFU, and an opportunity to practice kit use, including with the SureCRIC, on a manikin model. Training will be conducted by [name]. Audio and video recording will be utilized for reference and use in data reduction and analysis (if applicable). Cameras will be positioned on tripods so as not to interfere with the training.

After completion of the training, the Human Factors Center will individually interview each participant using open-ended questions to garner subjective feedback on the training and instructional materials, as well as preparedness to perform SureCRIC-aided procedures.

3. Decay Period (minimum 60 minutes). After training, participants will be removed from the facility for a minimum of 60 minutes. Participants will then report to the testing facility at an agreed-upon time.

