4. Usability Testing (approximately 30 minutes). After returning to the testing facility, participants will utilize the SureCRIC to perform various scenarios. A *Nasco Life/Form Cricothyrotomy Simulator* will be placed at the head of a table, fitted with a laryngeal insert, and covered with elastomeric "skin." The tool kit and packaged SureCRIC will be placed by the simulator. A new laryngeal insert and skin will be used for each scenario.

Manikin scenarios will include the following:

- Scenario #1: Direct percutaneous approach with Rusch QuickTrach Cricothyrotomy Kit
- Scenario #2: Seldinger approach with Melker Emergency Cricothyrotomy Catheter Set
- Scenario #3: Direct scalpel incision with North American Rescue Tactical Crickit

Each session will be observed by at least one Human Factors Center moderator, who will only be present to observe and give instructions and will not help participants with task completion in any way. Audio and video recording will be utilized for post-hoc data analysis. NCHFH staff will observe each manikin procedure focusing on usability and potential interference of the SureCRIC with the cricothyrotomy tools. NCHFH staff will additionally observe performance of critical tasks and essential tasks, focusing on the steps up to and including the step where the SureCRIC is removed from the manikin.

- 5. Semi-structured Interviews and Critical Error Debriefing (~15 minutes). Human Factors Center moderators will follow up with participants on any critical errors, close calls, or confusion/difficulty observed during task completion to determine the participant's perspective on the root cause of the error(s). Feedback will also be collected regarding perceived difficulty and usability of the device and IFU. Time is allotted for the moderator to ask the participants open-ended questions regarding their overall impressions of the SureCRIC, whether any tasks were particularly difficult to perform, whether training was adequate and how it might be improved, use of instructions during testing, and thoughts about SureCRIC use in the field. Participants will report on interference of the SureCRIC with his/her intended use of the cricothyrotomy tools.

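### Manikin users may be recruited through InnoVital's clinician network, and no rule excludes or records ties to the company, although the primary endpoint is those users' own report

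*Combined protocol and SAP*

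**What the plan says.** **Recruitment.** Section V.1 opens with "Recruitment of participants and subjects will be conducted through" and names three routes: third-party recruiting companies, training centers and schools, and "c) NCHFH and/or InnoVital clinician networks". It sets no limit on any route and does not separate the human study from the manikin study.

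**InnoVital's role.** Section I.2 states that "InnoVital Systems, Inc. (InnoVital) has engaged the National Center for Human Factors in Healthcare (Human Factors Center) to conduct the validation".

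**Manikin design and endpoint.** Section III.2 says: "The study will be a single-arm, open label study". The primary endpoint in section I.2 is "user-reported interference of the SureCRIC with the tools used for cricothyrotomy". It is collected at the interview after testing (III.2, step 5): "Participants will report on interference of the SureCRIC with his/her intended use of the cricothyrotomy tools". Interference documented by staff is listed in I.2 as a secondary endpoint.

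**Eligibility.** Section II.1 bars participants who took part in formative work or already know the device. Section II.4 adds, for novices, exclusions on teaching, recent training, recent or repeated performance of the procedure, earlier participation in related studies, and physical impairment. For experienced users, apart from the minimum age that applies to everyone, the only exclusion listed is earlier exposure to the SureCRIC.

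**The concern.** In a single-arm, open-label study with a self-reported primary endpoint, the credibility of the result depends on how freely users speak about problems with the device. A user who works for, advises, collaborates with or is related to someone at the company behind the evaluation has a reason to play problems down. The eligibility rules ask whether someone has met the device. They do not ask whether that person has a relationship with the company. An adviser or collaborator who has never handled the SureCRIC therefore passes every listed criterion.

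At stake is under-reporting of interference in the manikin primary endpoint. The study is descriptive, so no type I error or power is affected. What could suffer is the completeness of the list of interference problems that the study exists to produce.

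**Working it through.** The plan gives no figure for the share of users from each recruitment route, so there is nothing to reproduce on that point. The check is a reading of the relevant sections, plus simple proportions.

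**Step 1. Is the route open to manikin users?** Yes. V.1 covers participants in general, and no other section narrows it for the manikin study.

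**Step 2. Does any rule deal with ties to the company?**

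| Section | What it controls | Covers ties to InnoVital? |
|---|---|---|
| II.1 | Formative participation, familiarity with the device, atypical cricothyrotomy expertise | No |
| II.4, novices | Teaching, training, performance, related studies, impairment, device exposure | No |
| II.4, experienced users | Device exposure | No |
| III.2, step 1 | Background data; the examples are handedness, clinical experience, training and past procedures | Not among the examples |

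**Step 3. Does the primary endpoint depend on the user's own account?** Yes, according to I.2 and III.2, step 5.

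**Step 4. How many users could be involved?** The protocol gives two counts.

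- Section I.1: 15 novices + 2 experienced = 17 users. With three procedures each, 17 × 3 = 51, which reproduces the number of scenarios stated there.
- Section II.1: 18 novices + 3 experienced = 21 users, so 21 × 3 = 63 scenarios. Section II.3 also gives three experienced users.

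The two counts need reconciling, but that is a separate matter. With no cap, the number recruited through the InnoVital network can be anywhere from 0 to 17, or from 0 to 21.

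**Step 5. What weight does one tied recruit carry?**

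| Group | Section I.1 count | Section II.1 count |
|---|---|---|
| Experienced users | 1/2 = 50% | 1/3 = 33% |
| All manikin users | 1/17 = 5.9% | 1/21 = 4.8% |

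Section II.3 says the experienced users are included at FDA's request, to notice what novices may miss. They are the smallest group, they have the fewest exclusions, and they are clinicians of the kind a clinician network could plausibly supply.

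**Step 6. Can the bias be sized?** No. If a share s of users has a tie, and they leave out a fraction u of the interference that others would report, reports fall by s × u, given equal true rates in both groups. The documents give neither s nor u. Each can lie between 0 and 1, so the product can too. Any single percentage would come from assumed inputs.

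**The case against.** The strongest reply is that interference has a second source. Staff watch every manikin procedure with interference in mind, sessions are recorded, moderators follow up at debriefing on errors and difficulties they saw, and the analysis in III.2 promises a description of all interference and usability issues. A visible problem that a user does not mention could therefore surface as a gap between the staff and user accounts. This stands, and it rules out saying that nothing planned would reveal under-reporting. It does not remove the concern. Staff observation is only a secondary endpoint, and it is less likely to pick up interference that the user feels but an observer cannot see. Without the recruitment channel, a gap between the two accounts could not be related to ties.

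It is also fair to say that the InnoVital network is one route of three, joined by and/or, and that nothing shows it will be used or that its members have a stake in the device. For novices, who are 15 of 17 or 18 of 21 users, the exclusions on teaching and related studies narrow the pool of likely collaborators. Both points stand, so the concern is about what the plan permits.

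A reader might infer that V.1 contradicts section II.5. It does not. Where II.5 says "Third-party recruiters and administrative staff will coordinate logistics of participants and subjects", it governs contact handling, whereas V.1 governs where people are found. The rule "No hospital or health system employees will be included as subjects" is an eligibility rule that applies whatever the route, and the documents do not describe who belongs to either network.

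A reader might also extend the point to the human study. There the primary endpoint is pass or fail as verified by an expert (I.2), participants are randomly assigned to groups (II.1), and the volunteers whose necks are examined give no usability reports. The argument about a self-reported primary endpoint does not carry over.

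**Conclusion.** The point holds for the manikin study. The protocol allows users to be recruited through InnoVital's clinician network, and neither excludes nor records ties to the company, while the primary endpoint is open-label self-report. Users with such ties could under-report interference, and staff observation offsets this only in part. The effect is largest for the experienced users, where one tied recruit is 33% to 50% of the group. Across all manikin users, one recruit is about 5% to 6%.

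The conclusion rests on two assumptions. One is that InnoVital has an interest in a favorable result; the documents do not literally call it the manufacturer, but it commissioned the validation and obtained the FDA feedback on which the methods are based (I.2). The other is that a tie makes a user less ready to report problems, which is plausible but not shown here. The documents do not support a claim that tied users will in fact be enrolled, or any numerical estimate of the bias. The change is worth making because it costs little and protects a stated primary endpoint.

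**What to change.** 1. In section II.4, add an exclusion for manikin participants, both novice and experienced: employees, paid advisers, collaborators and family members of InnoVital.
2. At the telephone screening (II.1) or the pre-evaluation interview (III.2, step 1), ask about employment, advisory, financial and family ties to InnoVital, and record the recruitment channel. A category code is enough, so no identifying information is added.
3. In the raw data tables planned under the manikin data analysis (III.2), list the channel for each participant beside user-reported and staff-observed interference, so that any gap can be read against the source of recruitment.

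No change is needed to the volunteer subjects in the human study or to the Human Factors Center's own network. The cost is one exclusion line, one or two interview questions, one table column and a slightly smaller pool of experienced users. The documents do not show how many suitable experienced users the other routes would yield, so that last cost cannot be put in numbers.

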#### 2 Process of Consent.

After participants and subjects have arrived at the study site, they will be given an informed consent letter. After an opportunity to read the information and ask any questions, they will sign the form. Video recording will begin only after participants have signed the consent form. For participants that are hospital employees, they will be instructed that participation, or lack of participation will have no ill effects on their employment.

## **Payment for Participation.**

Control Group participants in the human study will be compensated \$125 for participation of approximately 1 hour. Experimental Group participants in the human study will be compensated \$175 for participation of approximately 2.5 hours. Subjects in the human study will be compensated approximately \$30/hour, and will be present on 4 consecutive, 9-hour days, and therefore be compensated \$1,080 each. One back-up subject will be recruited for each size and compensated \$75 per day of being "on call." In the manikin study, novice participants will be compensated \$225 for participation, and expert participants will be compensated \$750. The expert, verifier clinician will be compensated at a rate of \$250/hr. For 4 consecutive, 9-hour days, the expert verifier will be compensated a total of \$9,000.

